12.5 Secondary Analysis

We will also explore the impact of the mobile app on a variety of swallowing outcomes including diet level, patient perception, and physiological measures. Analysis of these endpoints will be carried out using logistic regression comparing arms A and B.

(aa) 12.5.1 Analysis Population

Analysis will include all participants.

(bb) 12.5.2 Analysis Plan

As above

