8.1 Primary Outcome Measure

Adherence to prescribed exercise protocol

(a) 8. 1.2 Measurement Definition

Overall adherence to prescribed exercise protocol measured as percentage of prescribed exercises completed over a seven-week period. (i.e. if participants are asked to complete 6 sets of 10 reps of each exercise daily for seven weeks, maximum potential would be 420 reps).

(b) 8.1.3 Measurement Methods

Participants will be asked to complete and log their swallow exercises using the either the Vibrent application or paper forms throughout the duration of radiation therapy and for 1 month after the completion of therapy. The Vibrent application will time stamp the date and time of data entry for secondary analysis to determine whether logging occurs on a daily basis or in batch. Paper logs will be collected by study personnel weekly and entered into a central Redcap database.

(c) 8.1.4 Measurement Time Points

Adherence measures will be obtained at the conclusion of the 7-week treatment period.

8.2a Secondary Outcome measures (These measures, in combination, provide a comprehensive evaluation of swallowing physiology, its functional impact, and patient perception.)

Patient reported:

MD Anderson Dysphagia Inventory (MDADI)

(d) 8.2a.2 Measurement Definition

The MD Anderson Dysphagia Inventory (MDADI) was selected to capture and quantify the patient perception of swallowing dysfunction. It is a 20-item patient reported survey that

measures the impact of dysphagia on patients with HNC. Each item is scored on a 5 point scale with 1=lower function and 5=higher function. Possible scores range from 20-100 with higher scores indicating more normal swallowing function. Mean scores will be assessed for each treatment group at the time of each assessment. Standard deviation and 95% CI will be reported.

(e) 8.2a.3 Measurement Methods

MDADI: Each item is rated on a scale of 1-5 with lower numbers indicating poorer function. Mean subscale scores are multiplied by 20 to provide a final score between 20-100. All participants will complete on paper forms.

(f) 8.2a.4 Measurement Time Points

Please see study schedule for the measurement time points.

8.2b Secondary Outcome measure

Functional Oral Intake Score (FOIS)

(g) 8.2b.2 Measurement Definition

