In order to describe patient diet levels, the Functional Oral Intake Scale was selected. The FOIS is a 7-point ordinal scale used to describe oral intake where lower scores reflect more limited oral intake and higher scores reflect more normal diet levels. The mean group FOIS score will be reported as well as standard deviation and 95% CI at each assessment (see study calendar).

(h) 8.2b.3 Measurement Methods

FOIS score will be given by the treating clinician based on patient reported diet level.

(i) 8.2b.4 Measurement Time Points

Please see study schedule for the measurement time points.

8.2c Secondary Outcome measure

Performance Status Scale – Head and neck (PSS HN)

(j) 8.2c.2 Measurement Definition

The Performance Status Scale – Head and Neck (PSS-HN) was chosen to provide additional detail regarding diet and eating restrictions. The three items which will be administered include "eating in public", "understandability of speech", and "normalcy of diet". Each item ranges from 0-100 with higher numbers reflecting more normal function. The mean group score will be reported as well as standard deviation and 95% CI at each assessment (see study calendar).

(k) 8.2c.3 Measurement Methods

PSS-HN will be completed by the treating clinician based on patient reports.

(1) 8.2c.4 Measurement Time Points

Please see study schedule for the measurement time points.

8.2d Secondary Outcome measure

Functional measures obtained during videofluoroscopic swallowing studies (VFSS)
Penetration Aspiration Scale (PAS)

(m)8.2d.2 Measurement Definition

In order to measure physiologic swallow function during MBS studies, three assessment tools were chosen. The Penetration Aspiration Scale is an 8-point interval scale used to describe degree of bolus entry into the laryngeal vestibule and patient response to this material. Higher numbers reflect more severe laryngeal penetration/aspiration. The mean group score for most severe PAS will be reported as well as standard deviation and 95% CI at each assessment (see study calendar).

(n) 8.2d.3 Measurement Methods

MBS ratings (PAS, MBS-Imp, DIGEST) will be rated by clinicians blinded to group assignment based on review of videotaped assessments.

8.2d.4 Measurement Time Points

Please see study schedule for the measurement time points.

8.2e Secondary Outcome measure

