Functional measures obtained during videofluoroscopic swallowing studies (VFSS) Individual item and composite scores of the Modified Barium Swallow Impairment Profile (MBS-ImP)

(o) 8.2e.2 Measurement Definition

The Modified Barium Swallow Impairment Profile is a tool designed to quantify degree of impairment on 13 individual physiologic components visualized during a modified barium swallow where higher numbers reflect greater dysfunction. The mean group score for the composite oral component and pharyngeal component will be reported as well as standard deviation and 95% CI at each assessment (see study calendar).

(p) 8.2e.3 Measurement Methods

MBS ratings (PAS, MBS-Imp, DIGEST) will be rated by clinicians blinded to group assignment based on review of videotaped assessments.

(q) 8.2e.4 Measurement Time Points

Please see study schedule for the measurement time points.

8.2f Secondary Outcome measure

Functional measures obtained during videofluoroscopic swallowing studies (VFSS)

Dynamic Imaging Grade of Swallowing Toxicity (DIGEST) severity scores

(r) 8.2f.2 Measurement Definition

The Dynamic Imaging Grade of Swallowing Toxicity was established to rate the safety and efficiency of the pharyngeal swallow during modified barium swallow studies using the National Cancer Institute's Common Terminology Criteria for Adverse Events (CTCAE) framework. This scale provides a safety impairment score, an efficiency impairment score, and an overall score. Lower numbers on this scale are indicative of more normal function. The mean group impairment scores will be reported as well as standard deviation and 95% CI at each assessment (see study calendar).

(s) 8.2f.3 Measurement Methods

MBS ratings (PAS, MBS-Imp, DIGEST) will be rated by clinicians blinded to group assignment based on review of videotaped assessments.

(t) 8.2f.4 Measurement Time Points

Please see study schedule for the measurement time points.

8.2g Secondary Outcome measure

Maximal interincisal opening

(u) 8.2g.2 Measurement Definition

Maximal interincisor distance will be reported in mm as the space between the bottom of the upper incisor and the top of the lower incisor. In patients missing dentition, 10mm will be deducted from this value for each missing incisor to represent the average incisal height.

(v) 8.2g.3 Measurement Methods

Standard mm measuring tools will be used.

(w) 8.2g.4 Measurement Time Points

Please see study schedule for the measurement time points.

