10.4 Primary Analysis

Analysis of the primary endpoint (adherence) will be carried out using logistic regression, comparing arms A and B. Analysis of the secondary adherence endpoint will be carried out using a linear mixed effect model with weekly adherence as a dependent variable, a patient-specific random intercept, treatment arm as the primary predictor, and week as a fixed (categorical) effect.

(y) Analysis Population

Analysis will include all participants.

(z) Analysis Plan

As above

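### Every swallowing outcome is assigned logistic regression with no stated form, cut-off or baseline term; a baseline-adjusted model at Week 19 would use data already collected

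*Combined protocol and SAP*

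**What the plan says.** Section 12.5 introduces the swallowing outcomes together: "We will also explore the impact of the mobile app on a variety of swallowing outcomes including diet level, patient perception, and physiological measures". The model follows: "Analysis of these endpoints will be carried out using logistic regression comparing arms A and B". The synopsis and section 10.1 repeat this, and 12.5.2 only refers back to it.

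The outcomes differ in type (sections 4 and 8.2):

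- Quantitative: MDADI (20-100), MBS-ImP oral and pharyngeal composites, interincisor distance (mm).
- Ordered: FOIS (7 levels), PAS (8 points, described as an interval scale), DIGEST scores, three PSS-HN items (each 0-100).

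Section 8.2 plans summaries by group. For MDADI: "Mean scores will be assessed for each treatment group at the time of each assessment. Standard deviation and 95% CI will be reported". FOIS, PSS-HN, worst PAS, the MBS-ImP composites and DIGEST are treated alike, for example "The mean group score for most severe PAS will be reported as well as standard deviation and 95% CI". Interincisor distance has no such statement.

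Pre-study values are collected for all of these (sections 4 and 7). Aim 2 is set at three months after treatment in the synopsis and section 1.2, which is Week 19 in the calendar. Section 4 restates Aim 2 without the time point, and 12.5 names no visit.

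The plan does name a linear model elsewhere, for weekly adherence: "linear mixed effect model with weekly adherence as a dependent variable, a patient-specific random intercept, treatment arm as the primary predictor" (10.4).

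**The concern.** Logistic regression may mean a binary model, which needs a split, or an ordinal (cumulative-logit) model, which does not. The plan does not say which. For MDADI, the MBS-ImP composites and interincisor distance, the binary reading discards information and depends on a cut that is not given.

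Both readings yield odds ratios, while section 8.2 describes the groups by means, so no between-arm difference on the reported scale is planned. Both also leave out the baseline score, which is available at no extra cost and is likely to predict the outcome.

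Two things are at stake for Aim 2, the comparison of arms on dysphagia. One is precision. The other is whether a reader can tell a planned result from one found by choosing among cuts.

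**Working it through.** **1. The plan's own figure.** The only sample-size figure is 88 per arm, for adherence (12.6). With a difference of 15, SD 32, 80% power and an assumed two-sided 0.05:

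n = 2 × (1.960 + 0.842)² × 32² / 15² ≈ 71.4, so 72 per arm; the t-test version gives 72.4, so 73.

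Adding 20%: 72 × 1.2 = 86.4 (87) or 73 × 1.2 = 87.6 (88). The figure reproduces as a comparison of two means for adherence. No sizing is offered for any swallowing outcome.

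**2. Assumptions for the illustration.** The documents give no effect size, SD or baseline correlation for these outcomes. Assumed: normal outcome, two-sided 0.05, standardised difference d, baseline correlation r of 0.2 to 0.6. Evaluable patients: 88 × 0.8 = 70.4, so 70 per arm. This borrows the dropout allowance of the primary endpoint, which ends at seven weeks; loss by Week 19 may differ. Reading the 20% as an addition gives 88 / 1.2 = 73.

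**3. Methods.**

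- Means: two-sample t-test power at d.
- Baseline-adjusted means: the same, with d replaced by d / √(1 − r²).
- Ordinal logit: rank score test, by simulation.
- Binary split at k: proportions 1 − Φ(k) and 1 − Φ(k − d), logistic Wald test, by simulation.

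Binary splits at d = 0.5, 70 per arm:

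| Cut | Control vs shifted arm | Power |
|---|---|---|
| Control median | 0.50 vs 0.69 | 64% |
| Midway between arm means | 0.40 vs 0.60 | 66% |
| Pooled median | set by the data | 69% |
| 20% of controls above | 0.20 vs 0.37 | 59% |
| 80% of controls above | 0.80 vs 0.91 | 43% |

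**4. Power by model, 70 per arm.**

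| d | Binary, across these cuts | Ordinal | Means | Baseline-adjusted means |
|---|---|---|---|---|
| 0.5 | 43-69% | 82% | 84% | 85-96% |
| 0.4 | 30-51% | 63% | 65% | 67-84% |
| 0.3 | 20-33% | 40% | 42% | 44-60% |

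At 73 per arm and d = 0.5: 45-69%, 83%, 85%, 86-96%. The ordinal reading therefore costs about 2 points against means. Any further gain comes from the baseline term; a rank-based baseline-adjusted analysis gives 83-94% at d = 0.5.

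**5. Ordered scales.** Assume seven equally filled control levels and 70 per arm. With a common odds ratio of 2.5, the ordinal model and a comparison of mean scores both give 86%, against 29-77% over the six binary cuts. With a latent normal shift of 0.5, where proportional odds does not hold, both give 80%, against 31-65%. Ordinal model or mean difference is thus a choice of scale, not of power.

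**6. Open cut-off.** With no true difference and 70 per arm, the chance that at least one cut reaches p<0.05 is 12% for three cuts (20/50/80%), 18% for the six cuts of a seven-level scale, and 19% for seven cuts of a quantitative scale. One fixed model gives 5%.

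**The case against.** The strongest reply is that these analyses are labelled exploratory, claim no power, and compare randomised arms. An unadjusted logistic comparison is valid, so leaving out baseline is lost efficiency, not an error. That stands and sets the weight of the point. It does not remove it: the outcomes are the secondary objective (1.2) and are titled secondary outcome measures (8.2).

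The magnitudes are also assumed. The 43% comes from an extreme cut that nobody proposed; central cuts give 64-69%. The 12-19% arises only if several cuts are tried and any success is kept, and nothing in the documents says that will happen.

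Four stronger readings are tempting and are not supported:

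- A reader might infer that the gap is peculiar to the swallowing outcomes. It is not. Section 10.4 also assigns logistic regression, with no stated form, to the primary adherence percentage; only weekly adherence has a linear model.
- A reader might infer that the visits other than Week 19 have no role. Section 8.2 gives them a descriptive one, at each assessment, for everything except interincisor distance. What they lack is a place in the comparison of arms.
- A reader might infer that the Aim 2 time point is missing. It can be found from section 1.2 and the calendar; it is merely not repeated in section 4 or 12.5.
- A reader might infer that Aim 2 tests whether better adherence improves swallowing. Aim 2 compares arms; the adherence link is a hypothesis in section 2.3.

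The body of Appendix J (DIGEST) is not in the text available here, so remarks on DIGEST grading are limited to section 8.2f.

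**Conclusion.** The point holds as one of efficiency and credibility, not validity or sizing, and should be addressed. One unspecified logistic model covers quantitative and ordered outcomes, and baseline is left out of every comparison of arms.

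Under the assumptions above, with d = 0.5, a central binary split costs about 15 to 20 points of power against a comparison of means (64-69% against 84%). An ordinal model costs about 2. Baseline adjustment adds between 1 and 12 points to the 84%, depending on r. These figures show what the open choices are worth; they do not forecast this trial.

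The visit not repeated in 12.5, the undefined dysphagia prevalence and the unstated role of the MBS-ImP individual items are missing detail. They would not carry the point alone.

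**What to change.** In the synopsis, 10.1 and 12.5:

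- **MDADI, MBS-ImP oral and pharyngeal composites, interincisor distance:** linear regression (ANCOVA) at Week 19 with arm and baseline value, reporting the adjusted mean difference and 95% CI.
- **FOIS, worst PAS, DIGEST, PSS-HN items:** a model with arm and baseline score, either proportional-odds regression or a baseline-adjusted mean difference. The first relies on the proportional-odds assumption and leaves odds ratios beside descriptive means; the second matches section 8.2. Name one before data are examined by arm.
- **Dysphagia prevalence:** keep binary logistic regression for this only, with scale, cut and visit chosen by the investigators and fixed before data are examined by arm.

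As tidying: repeat the Week 19 visit in section 4 and 12.5, label the other visits supportive, and say whether the MBS-ImP individual items are descriptive.

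The cost is analysis wording. Baseline and Week 19 values are already in the study calendar, so no visit, measure or patient is added.

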12.6 Sample Size

(cc) 12.6.1 Accrual estimates

Accrual estimates are based upon average clinical volumes at three participating institutions over the past 3 years.

(dd) 12.6.2 Sample size justification

88 patients will be enrolled in each arm. This number will provide 80% power to detect a 15 percentage point difference between groups. This sample size includes the addition of 20% to account for anticipated drop out.

(ee) 12.6.3 Effect size justification

This calculation is made assuming 33% adherence in arm B and a standard deviation of 32 based on prior studies.

Appendix C: Patient Comfort with Technology

1. Do you own either a	an Android or Apple-iOS based s	smartphone or tablet?
Yes	□No	
Do you have access plan (~200MB/montl	s to an internet connection or a s h) or greater?	sufficient monthly data
Yes	□No	
3. Please mark on the	line to indicate your comfort us	ing technology.
Very uncomfortable		Very comfortable
4. Please mark on the	line to indicate your comfort us	ing your smartphone.
Very uncomfortable		Very comfortable
	line to indicate your comfort us	
Very uncomfortable		Very comfortable

Appendix D: Paper logging form

Exercise logging form: Please indicate the number of sets of exercises prescribed you completed and denote your level of pain after completing the sets of exercises with 1 being no pain, and 10 extreme:

	Day 1	Day 2	Day 3	Day 4	Day 5	Day 6	Day 7
Date							
AM							
PM							
Pain Level (1- 10)							

Appendix E: MD Anderson Dysphagia Inventory

This questionnaire asks for your views about your swallowing ability. This information will help us understand how you feel about swallowing.

The following statements have been made by people who have problems with their swallowing. Some of these statements may apply to you.

Please read each statement and circle the response which best reflects your experience in the past week.

F1	My swallowing	ability lir	mits my day to	dav activitie	
	Strongly Agree	Agree	No opinion	Disagree	Strongly Disagree
E2.	l am embarras	sed by my	_		
	Strongly Agree	Agree	No opinion	Disagree	Strongly Disagree
F1.	People have d	ifficulty co		•	
	Strongly Agree	Agree	No opinion	Disagree	Strongly Disagree
P2.	_			•	
	Strongly Agree	Agree	No opinion	Disagree	Strongly Disagree
E7.					0
	Strongly]Agree	Agree	No opinion	Disagree	Strongly Disagree
E4.		-			0
	Strongly Agree	Agree	No opinion	Disagree	Strongly Disagree
P6.		_		B:	0
	Strongly Agree	Agree	No opinion	Disagree	Strongly Disagree
E5.					
	Strongly Agree	Agree	No opinion	Disagree	Strongly Disagree
E7. E4.	Agree Swallowing is Strongly Agree I do not feel se Strongly]Agree I am upset by Strongly Agree Swallowing tal Strongly Agree I do not go out Strongly	more diffi Agree elf-conscio Agree my swallo Agree kes great	cult at the end No opinion ous when I eat No opinion owing problem No opinion effort. No opinion	l of the day. Disagree Disagree Disagree Disagree	Strongly Disagree Strongly Disagree Strongly Disagree Strongly Disagree Strongly Disagree

F5. My swallowing difficulty has caused me to lose income. Strongly Agree No opinion Disagree Stronaly Agree Disagree P7. It takes me longer to eat because of my swallowing problem. No opinion Disagree Stronaly Strongly Agree Agree Disagree P3. People ask me, "Why can't you eat that?" Agree No opinion Strongly Disagree Strongly Agree Disagree E3. Other people are irritated by my eating problem. No opinion Stronaly Stronaly Aaree Disagree Agree Disagree P8. I cough when I try to drink liquids. Agree No opinion Disagree Strongly Strongly Agree Disagree F3. My swallowing problems limit my social and personal life. Strongly Agree No opinion Disagree Strongly Agree Disagree F2. I feel free to go out to eat with my friends, neighbors, and relatives. Strongly Agree No opinion Disagree Strongly Disagree Agree P5. I limit my food intake because of my swallowing difficulty. Strongly Agree No opinion Disagree Stronaly Agree Disagree P1. I cannot maintain my weight because of my swallowing problem. Stronaly Aaree No opinion Disagree Stronaly Agree Disagree E6. I have low self-esteem because of my swallowing problem. Strongly Agree No opinion Disagree Strongly Agree Disagree P4. I feel that I am swallowing a huge amount of food. Strongly Agree No opinion Disagree Strongly Agree Disagree F4. I feel excluded because of my eating habits. Strongly Agree No opinion Disagree Strongly Agree Disagree

Appendix F: Functional Oral Intake Scale (FOIS)

- Level 1: Nothing by mouth
- Level 2: Tube dependent with minimal attempts of food or liquid
- Level 3: Tube dependent with consistent oral intake of food or liquid
- Level 4: Total oral diet of a single consistency
- Level 5: Total oral diet of multiple consistencies but requiring special preparation or compensations
- Level 6: Total oral diet of multiple consistencies without special preparation but with specific food limitations
- Level 7: Total oral intake without restrictions

Appendix G: Performance Status Scale – Head and Neck

Eating in Public
No restriction of place, food, or companion (eats out at any opportunity) (100)
No restriction of place but restricts diet when in public(eats anywhere but may limit intake
to less "messy" foods, e.g. liquids) (75)
Eats only in presence of selected persons in selected places (50)
Eats only at home in presence of selected persons (25)
Always eats alone (0)
Understandability of speech
Always understandable (100)
Understandable most of the time; occasional repetition necessary (75)
Usually understandable; face to face contact necessary (50)
Difficult to understand (25)
Never understandable; may use written communication (0)
Normalcy of diet
Full diet (no restrictions) (100)
Peanuts (90)
All meat (80)
Carrots, celery (70)
Dry bread and crackers (60)
Soft, chewable foods (e.g. macaroni, canned/soft fruits, cooked vegetables, fish,
hamburger, small pieces of meat) (50)
Soft foods requiring no chewing (e.g. mashed potatoes, applesauce, pudding) (40)
Pureed foods (in blender) (30)
Warm liquids (20)
Cold liquids (10)
Nonoral feeding (tubefed) (0)

Appendix H: Penetration Aspiration Scale

Score	Characteristics
1	Does not enter airway
2	Enters airway, remains above cords, is ejected
3	Enters airway, remains above cords, not ejected
4	Enters airway, contacts cords, is ejected
5	Enters airway, contacts cords, not ejected
6	Enters airway, below cords, ejected out or into larynx
7	Enters airway, below cords, not ejected despite effort
8	Enters airway, below cords, no effort to eject

[figure not shown]
Appendix I: Modified Barium Swallow Impairment Profile (MBS-Imp)

MBSlimP**© Balus Specific Scoring Grid	(har eg	dans)	use in sco	ing practi	be-\$1	raining)	Clin	kten;_				_
Patient Name												
Detr												
	_			- Las	ULV	ev-				LAP	MEN	l
COMPONENT	This				Sacta		Banqu	Problem	Solid	Sector	Publing	0 I Scores
	Simil Top.		Custolled Single Sp					5 ni 14.	Ti pokin II. Sni Pubbig		S ni Tip.	
1. Lip Closum (I -4)		П			Г							
2. Tongue Control during Balus Hold (0 - 1)												
Belia PrepMastication (0 - 3)												
4. Bolos TransportLingual Motion (II - 4)												
5. Oral Residue (D-4)												
5. Initiation of Pharyngeol Sirollow (0 - 4)												
7. Soft Polide Beradion (0-4)					Г							
II. Laryngeal Elevation (6-1)												
Anterior Hyold Movement: (0 - 2)												
10. Epiglottic Novement (0-2)												
H. Laryngeal Vestibular Closure (4 - 2)												
12. Pharyngeol Stripping Neve (6-2)												
13. Pharyngeal Contraction (9-3)												
18. PES Opening (6 - 3)												
15. Tongue Base Retraction (6 - 4)												
15. Pharyngeol Besidue (0-4)												

per even

17. Esophageal Clearance Upright Position (8 - 4)

